### 12.8 Efficacy Analyses

All efficacy outcomes will be analyzed in the ITT population. Only the primary and secondary efficacy endpoints will be analyzed in the PP population as supportive analyses, as summarized in the Table below.

Efficacy Endpoints	Primary	Sensitivity Analysis
Efficacy Enapoints	1 1 1111ttl y	Schister vicy randingsis

	Analysis	
Discoura Parla sint		ITT, OC
Primary Endpoint	ITT, MI	ITT, TF
PGA response at Week 12		ITT, LOCF
		PP, OC
Secondary Endpoints	ITT, MI	ITT, OC
Categorical Endpoint:	111,1,11	ITT, TF (categorical
PASI-75 at Week 12		endpoint)
• PGA 0 or 1 at Week 12		ITT, LOCF
PASI-90 at Week 12     PASI-90 at Week 12		PP, OC
Continuous Endpoint:		
Change in %BSA at Week 12		
-	ITT, OC	N/A
Exploratory Endpoints	111,00	IN/A
Time to PGA response	TTTT 3.67	TTTT 0.0
Exploratory Endpoints	ITT, MI	ITT, OC
• PGA 0 or 1 at Weeks 2, 4, and 8		

 
PGA response at Weeks 2, 4, and 8
 
		
• Change in PASI from Baseline at Weeks 2, 4, 8, and		
12		
• % change in PASI from Baseline at Weeks 2, 4, 8,		
and 12		

 
PASI-50 at Weeks 2, 4, 8, and 12
 
		

 
PASI-75 at Weeks 2, 4, and 8
 
		

 
PASI-90 at Weeks 2, 4, and 8
 
		
• Change in %BSA from Baseline at Weeks 2, 4, and 8		
• % change in %BSA from Baseline at Weeks 2, 4, 8,		
and 12		
Other Endpoints	ITT, OC	N/A

 
Change from Baseline in Peak NRS at Weeks 2, 4,
 
		
6, 8, 10, 12 and 16		

 
% change from Baseline in Peak NRS at Weeks 2, 4,
 
		
6, 8, 10, 12 and 16		

 
Peak NRS 4-point Responder at Weeks 2, 4, 6, 8, 10, 12 and 16
 
		
Change from Baseline in DLQI at Weeks 4, 12, and		
16		

 
% change from Baseline in DLQI Total Score at Weeks 4, 12 and 16
 
		
• Change from Baseline in PSD at Weeks 2, 4, 8, 12, and 16		

 
% change from Baseline in PSD Total Score at Weeks 2, 4, 8, 12 and 16
 
		
• Change from Baseline in SF36 at Weeks 4, 12, and 16		

# 12.8.1 Primary Efficacy Analyses

The primary efficacy endpoint will be analyzed using a Cochran–Mantel–Haenszel (CMH) test stratified by PGA score at Baseline (PGA scores of 2, 3 or 4) based on the ITT population using the multiple imputation approach.

- For each multiple imputation dataset, the CMH option in PROC FREQ will calculate the adjusted estimate of the common relative risk of success (tapinarof/placebo) over all strata with its 95% confidence interval (CI).
- The logit-based version of the estimate and its confidence bounds will be log-transformed and the SE of the estimate of the log(relative risk) will be back-calculated from the log(confidence bounds) by assuming an asymptotic normal distribution.
- The estimates of the log(relative risk) and their standard errors for all the multiple imputation datasets will be input to PROC MIANALYZE to test the null hypothesis that tapinarof is not different from placebo. The p-value of the combined results will be reported for interpretation.
- PROC MIANALYZE will output an overall estimate of the log(relative risk) and its 95%
   CI. These will be exponentiated to produce an overall estimate of the relative risk and its 95%
   CI.

Sensitivity analyses in the ITT population will be conducted in which missing values are not imputed, i.e., Observed Cases (OC), or imputed as treatment failures (TF), and efficacy is tested with the CMH statistic as described above. Supporting analyses of the primary endpoint will also be performed

- in the PP population based on OC only,
- in the ITT population with missing values imputed by LOCF,

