#### 10.4.2.1. Primary Endpoint Analyses

The primary efficacy endpoint is proportion of subjects who achieve PGA score of clear (0) or almost clear (1) with a minimum 2-grade improvement from Baseline at Week 12. The primary efficacy endpoint will be analyzed using a Cochran–Mantel–Haenszel (CMH) test stratified by PGA score at Baseline (PGA scores of 2, 3 or 4).

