## 10.6. Handling of Missing Data

Every effort will be made to collect complete data at all visits.

The primary method of handling of missing data will utilize Multiple Imputations (MI). For sensitivity analysis, Treatment Failure (TF) will be imputed for missing data.

For the MI model, 100 imputations will be generated using PROC MI of SAS. Fully Conditional Specification (FCS) model using the regression method will be used with the response (eg, PGA score) at prior post-baseline visits, baseline strata, and treatment group as covariates, The ROUND and MINIMUM options will be utilized to ensure imputed values are non-negative integers. The seed to be used is 20180330. The results of the 100 analyses will be transformed into a normal statistic and combined into a single analysis using PROC MIANALYZE.

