### 7. SAMPLE SIZE DETERMINATION

It is assumed that the proportion of subjects who achieve PGA score of clear (0) or almost clear (1) with a minimum 2-grade improvement from Baseline at Week 12 will be 40% for subjects receiving tapinarof compared with 15% for subjects receiving vehicle control. With 500 subjects randomized in a 2:1 ratio (approximately 333 subjects receiving tapinarof cream, 1% and approximately 167 subjects receiving vehicle cream) there will be > 99% power for statistical significance (2-sided p< 0.05). If tapinarof response rate is 35%, and vehicle response rate is 20%, the power will be > 94%. Power comes from a Fisher Exact sample size calculation which is conservative. It is assumed that up to 25% of the subjects will be lost to follow-up by 12 weeks. These subjects will be included in the primary analysis in the ITT population using the multiple imputation method as detailed below.

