### 12.7 Efficacy Endpoints

### 12.7.1 Primary Efficacy Endpoint

The primary efficacy endpoint is the proportion of subjects who achieve a Physician Global Assessment (PGA) treatment response, defined as a PGA score of clear (0) or almost clear (1) with a minimum 2-grade improvement from Baseline at Week 12.

The PGA is a static 5-point assessment of overall disease severity, as determined by the Investigator, ranging from 0 (clear) to 4 (severe).

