### 12.8.2 Secondary and Exploratory Efficacy Analyses

The same methods as discussed for the primary analyses will be used to analyze all dichotomized and continuous secondary endpoints. The secondary efficacy endpoints will be tested sequentially in the order listed. Testing will stop if non-significance (2-sided  $p \ge 0.05$ ) is observed as described in Section 11.6.

Other exploratory efficacy endpoints will be analyzed using CMH test for proportions, and analysis of covariance (ANCOVA) model for continuous variables. CMH tests will be stratified by baseline PGA score, and ANCOVA models will include baseline PGA score as a covariate (2, 3 or 4), and baseline value of the endpoint as a continuous covariate. For proportions, the same MI approach describe above will be taken to deal with missing data. For continuous variables, the standard MI procedures for ANCOVA will be followed. Least squared means of treatment difference (tapinarof – placebo) along with the 95% CI will be reported.

Time to achieving a PGA success will be analyzed with the Kaplan Meier method in the ITT population based on Observed Cases. Treatment groups will be compared using a log-rank test. Estimates of median time to response from Kaplan Meier distribution will be computed. A Kaplan-Meier figure will also be generated.

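### Minor: the primary relative risk and p-value use the logit (inverse-variance) estimate, which the small PGA 2 and PGA 4 strata pull towards 1; the Mantel-Haenszel estimate is a cheap improvement

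*SAP*

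**What the plan says.** SAP 12.8.1 calls the primary analysis a CMH test stratified by baseline PGA (2, 3 or 4). It then describes a Wald test. In each imputed dataset the common RR is estimated over the strata. "The logit-based version of the estimate and its confidence bounds will be log-transformed", a standard error is back-calculated from the bounds, and PROC MIANALYZE pools the 100 results. "The p-value of the combined results will be reported for interpretation".

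This agrees with Protocol 10.6: "The results of the 100 analyses will be transformed into a normal statistic and combined into a single analysis using PROC MIANALYZE". SAP 9 says the same.

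SAP 12.8.2 extends the method: "The same methods as discussed for the primary analyses will be used to analyze all dichotomized and continuous secondary endpoints". For the dichotomized ones this covers PASI-75, PGA 0 or 1, and PASI-90, which sit in the fixed testing sequence of SAP 11.6.

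For the observed-case (OC) and treatment-failure (TF) analyses, SAP 12.8.1 says "efficacy is tested with the CMH statistic as described above".

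SAP 6 limits PGA 2 and PGA 4 to about 10% each of the randomized population. Neither document gives response rates by stratum, or a rule for a stratum with a zero cell.

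**The concern.** An inverse-variance weight for a log RR depends on the responder counts, and so does the log RR itself. In a small stratum the two move together. If vehicle responders happen to be few, the stratum RR is high and its weight low; if they happen to be many, the RR is low and its weight high. The pooled RR is therefore too small on average when tapinarof works, and the test is conservative in the direction that matters.

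At stake are the accuracy of the reported RR and some power if the effect is smaller than planned. The loss can be larger for a rare secondary endpoint. Separately, the OC and TF wording can be read as the CMH chi-square or as the RR procedure just described, so two programmers could report different p-values.

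**Working it through.** **Inputs.** Two-sided 0.05 (SAP 11.1); 333/167, rates 40/15 and 35/20, loss up to 25% (SAP 7); 100 imputations (SAP 9). Strata (SAP 6): 10% of 500 = 50, split 2:1 as 33/17, for PGA 2 and for PGA 4; 80% = 400, split 267/133, for PGA 3. Check: 33 + 267 + 33 = 333 and 17 + 133 + 17 = 167.

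**The plan's own figure.** SAP 7: "If tapinarof response rate is 35%, and vehicle response rate is 20%, the power will be > 94" (per cent), from an unstratified Fisher exact calculation. Exact enumeration gives 93.8% at 333/167 and 94.0% at 334/167, and 99.998% at 40/15. The figures reproduce, but they do not describe the statistic in SAP 12.8.1. The 35/20 case is used below only as the plan's own less favourable scenario.

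**Formulas.** Stratum h has a responders of n1 active, c of n0 vehicle, N = n1 + n0 and m = a + c.
- Logit: L = ln[(a/n1)/(c/n0)], v = 1/a − 1/n1 + 1/c − 1/n0, w = 1/v. Pooled ln RR = Σ(wL)/Σw, variance 1/Σw.
- MH: RR = Σ(a·n0/N) / Σ(c·n1/N). Variance of ln RR = Σ[(n1·n0·m − a·c·N)/N²] / [Σ(a·n0/N)·Σ(c·n1/N)].

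**Mechanism.** At 20% a small stratum expects 17 × 0.20 = 3.4 vehicle responders. Take a = 12 of 33:
- c = 2: RR = 0.364/0.118 = 3.09; v = 0.083 − 0.030 + 0.500 − 0.059 = 0.494; w = 2.0.
- c = 5: RR = 0.364/0.294 = 1.24; v = 0.083 − 0.030 + 0.200 − 0.059 = 0.194; w = 5.1.

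Chance alone gives the lower RR about 2.5 times the weight. In the MH formula the coefficients of a and c (17/50 and 33/50 here) depend only on stratum sizes.

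**Power, complete data.** 200,000 simulated trials per case, with 0.5 added to a stratum with a zero cell (assumed rule). Overall rates are 35/20 throughout; stratum rates are assumed.

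| Small-stratum rates (tapinarof/vehicle, %) | MH | Logit | MH − logit |
|---|---|---|---|
| Constant RR: 35/20 in every stratum | 93.8 | 91.5 | +2.3 |
| Constant RR: PGA 2 8.75/5 | 94.1 | 92.6 | +1.5 |
| Constant RR: both 8.75/5 | 94.6 | 94.0 | +0.6 |
| Constant RR: both 3.5/2 | 95.0 | 94.5 | +0.5 |
| No effect: both 20/20 | 93.8 | 92.5 | +1.3 |
| No effect: both 10/10 | 94.2 | 94.4 | −0.2 |
| No effect: both 5/5 | 94.7 | 94.9 | −0.2 |
| Stronger effect: both 20/5 | 94.2 | 89.8 | +4.4 |
| Stronger effect: both 20/3 | 94.4 | 88.3 | +6.1 |
| Reversed: both 10/15 | 94.2 | 95.1 | −0.9 |
| Reversed: both 5/10 | 94.6 | 96.0 | −1.4 |

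Under a constant RR the top of the range is 2.5 if zero strata are dropped instead. At 40/15 both exceed 99.9%.

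**Estimate.** Median RR at 40/15: MH 2.68, logit 2.58, true 2.67 (2.58/2.67 = 0.966, about 3% low). At 35/20: MH 1.75, logit 1.71, true 1.75. At 40/15 the upper 95% limit falls below the true RR in 4.5% of trials (logit) and 3.1% (MH), nominal 2.5%; two-sided coverage is 94.5% and 95.2%.

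**Null, complete data.** Rejection in favour of tapinarof: logit 1.4% to 1.6%, MH 2.0% to 2.1% (nominal 2.5%). Two-sided: logit 4.2% to 4.6%, MH 4.7% to 4.8%.

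**With multiple imputation, 35/20 overall.** Sequential regression with rounding as in SAP 9 and random monotone dropout, under two assumed visit models:
- Exchangeable correlation 0.7, 100 imputations, 4,000 trials. Equal rates: 92.3% MH vs 89.1% logit at 10% missing, and 89.8% vs 86.4% at 25%. At 25% missing: PGA 2 8.75/5, 89.6% vs 87.3%; small strata 5/5, 89.0% vs 89.6%; small strata 20/3, 92.3% vs 86.1%.
- First-order autoregressive correlation 0.7, 25 imputations, 20,000 trials, constant RR. Equal rates: gain 2.8 points at 10% missing and 3.4 at 25%. Other stratum rates at 25% missing: gains of 1.0 to 4.0 points.

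**Rare endpoint.** At an assumed 12/4, complete data: MH 86.3%, logit 78.1%.

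**The case against.** The strongest reply is that nothing here is an error. The logit estimate is a standard choice, every step is written down, and the p-value and interval come from the same quantity and so agree. At the planning rates the choice does not affect the conclusion. All of that stands.

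The logit estimate also has the lower root mean squared error for the RR: 0.55 against 0.59 at 40/15, 0.31 against 0.33 at 35/20, and 1.2 against 2.4 at 12/4. On the log scale the MH penalty is only 1% to 3% at the primary-endpoint rates, so for the primary endpoint this is a small price. For a rare endpoint it is a real one, set against the power gain.

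The gain depends on rates the documents do not give. The response definition ("defined as a PGA score of clear (0) or almost clear (1) with a minimum 2-grade improvement from Baseline at Week 12") requires a PGA 2 subject to reach 0. A lower rate in that stratum is therefore likely, which moves the constant-RR gain towards the lower end. That stands too.

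Finally, the SAP is already at version 3.0 in a pivotal study, and changing the primary estimator has a credibility cost. That is a reason to make the change only while blinded and to document it.

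Three stronger readings are tempting and not supported:
- A reader might infer that the SAP departs from the protocol's CMH test. Protocol 10.6 itself foresees a normal statistic pooled by PROC MIANALYZE.
- A reader might infer that MH is never worse. It loses a little when the small strata show no effect at low rates, and more when the effect is reversed there.
- A reader might want a special rule for an arm without responders. For the primary endpoint the complete-data chance of none among 167 vehicle subjects at 15% is 0.85^167, about 2 × 10⁻¹². A switch to another statistic would allow the p-value and interval to disagree, which the present plan avoids.

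**Conclusion.** The point holds as a minor efficiency and accuracy improvement. The logit RR is about 2% to 3% too low at the median. Its complete-data rejection rate in favour of tapinarof under the null is about 1.4%, against about 2.0% for MH and a nominal 2.5%. Two-sided type I error is not inflated, a result near 40/15 is not at risk, and a positive finding under the current plan would be sound.

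At 35/20 with a constant RR, MH gains about 0.5 to 2.5 points of power with complete data and about 1 to 4 points with multiple imputation at 25% missing. The imputation range is the closer description of the planned analysis when loss reaches the plan's 25% limit. The gain is larger if the small strata show a stronger effect or the endpoint is rare. The loss is about 0.2 to 0.6 points if they show no effect at low rates, and about 1 to 1.5 points if the effect is reversed there.

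Stratum rates, the rare-endpoint rates, the visit model and the zero-cell rule are all assumptions. Absolute power under imputation varies with the visit model (MH 89.8% or 87.9% for equal rates at 25% missing), but the gap is about 3.4 points in both. The OC/TF wording is only a small clarification.

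**What to change.** Before unblinding, in SAP 12.8.1:
1. Name the Mantel-Haenszel estimate of the common RR in place of the logit-based one, for the primary and all dichotomized endpoints. Keep the log transformation, the back-calculated standard error and the PROC MIANALYZE step.
2. Add one sentence: *The OC, TF, LOCF and PP analyses report the same Mantel-Haenszel relative risk, its 95% CI and the Wald p-value on the log scale.* If the logit estimate is kept, the sentence is still needed, naming that estimate.

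Cost: one phrase, one sentence and a documented blinded amendment. The SAP's reference to a logit-based version implies that the same procedure also gives the MH version; this is assumed here. The p-value and interval stay consistent. The price is the slightly higher error of the RR (clearly higher for a rare endpoint) and the small power loss if the small strata show no effect or a reversed one. No separate fallback statistic is needed.

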### 12.8.2 Secondary and Exploratory Efficacy Analyses

The same methods as discussed for the primary analyses will be used to analyze all dichotomized and continuous secondary endpoints. The secondary efficacy endpoints will be tested sequentially in the order listed. Testing will stop if non-significance (2-sided  $p \ge 0.05$ ) is observed as described in Section 11.6.

Other exploratory efficacy endpoints will be analyzed using CMH test for proportions, and analysis of covariance (ANCOVA) model for continuous variables. CMH tests will be stratified by baseline PGA score, and ANCOVA models will include baseline PGA score as a covariate (2, 3 or 4), and baseline value of the endpoint as a continuous covariate. For proportions, the same MI approach describe above will be taken to deal with missing data. For continuous variables, the standard MI procedures for ANCOVA will be followed. Least squared means of treatment difference (tapinarof – placebo) along with the 95% CI will be reported.

Time to achieving a PGA success will be analyzed with the Kaplan Meier method in the ITT population based on Observed Cases. Treatment groups will be compared using a log-rank test. Estimates of median time to response from Kaplan Meier distribution will be computed. A Kaplan-Meier figure will also be generated.

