Tapinarof cream has been investigated in prior studies at concentrations from 0.5% to 8.0% and at once daily and twice daily dosing frequencies. The 1% concentration applied once daily was chosen as the dose and dosing frequency to take forward in the clinical development program based on the data from GSK Phase 2b clinical Study 203120. In that study, applications of tapinarof at concentrations of 0.5% and 1% applied once or twice daily were evaluated. Overall, both concentrations demonstrated an acceptable safety profile when applied once or twice daily. A faster onset of action was observed with 1% dosing groups compared with the 0.5% dosing groups in both studies; fast onset of action is an important consideration for topical medications. A once daily application regimen may reduce systemic exposure as the skin heals, thereby providing a better safety profile for a drug intended for long-term use to treat a chronic condition. In addition, once daily application may improve treatment adherence compared with more frequent dosing administrations. Based on the efficacy and safety data from Study 203120, 1% once daily was chosen as the tapinarof concentration and dosing frequency to be investigated in this study and intended for registration.

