### 11. DATA CONVENTIONS FOR ANALYSIS

### 11.1 General Statistical Principles

All statistical tests will be performed at the 0.05 (two-sided) level of significance.

All observed and derived variables (e.g., change from baseline, percentage change from baseline, and response status) that are analyzed or summarized will be listed by subject. Descriptive statistics will provide an overview of the efficacy and safety results. For categorical parameters, the number and percentage of subjects in each category will be presented. The denominator for percentage will be appropriate for the purpose of the analysis. For continuous parameters, descriptive statistics will include number of subjects, mean, standard deviation (SD), median, minimum, and maximum.

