### 12.7.3 Exploratory Efficacy Endpoints

The exploratory endpoints to further characterize the efficacy of tapinar of cream, 1% compared with vehicle control over time are:

- Time (days) to achieving a PGA treatment response, defined as days from date of first dose until achieving a PGA score of 0 or 1 with a minimum 2-grade improvement from Baseline. Subjects who have no PGA response will be censored at the date of their last PGA assessment.
- Proportion of subjects with a PGA score of 0 or 1 at Weeks 2, 4, and 8
- Proportion of subjects who achieve a PGA treatment response at Weeks 2, 4, and 8
- Mean absolute and percent change in PASI score from Baseline to Weeks 2, 4, 8, and 12
- Proportion of subjects with ≥ 50% improvement in PASI score (PASI-50) from Baseline to Weeks 2, 4, 8, and 12
- Proportion of subjects with ≥ 75% improvement in PASI score (PASI-75) from Baseline to weeks 2, 4, and 8
- Proportion of subjects with ≥ 90% improvement in PASI score (PASI-90) from Baseline to weeks 2, 4, and 8
- Mean change in %BSA affected from Baseline to Weeks 2, 4, and 8
- Mean % change in %BSA affected from Baseline to Weeks 2, 4, 8, and 12.

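### Exploratory responder endpoints at Weeks 2, 4 and 8 inherit the logit log-relative-risk pooling with no zero-cell rule, so their primary MI result can be undefined or much less powerful than the CMH test the SAP names

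*SAP*

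**What the plan says.** SAP 12.7.3 lists the early responder endpoints, among them "Proportion of subjects who achieve a PGA treatment response at Weeks 2, 4, and 8", together with PGA 0 or 1, PASI-75 and PASI-90 at the same weeks and PASI-50 at Weeks 2 to 12. The table in SAP 12.8 makes ITT with MI their primary analysis and ITT observed cases the sensitivity analysis.

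SAP 12.8.2 names the CMH test stratified by baseline PGA for these proportions, and then says: "For proportions, the same MI approach describe above will be taken to deal with missing data". The only pooling described above that sentence is in 12.8.1. There, each imputed dataset yields a logit-based common relative risk, its SE is worked back from the confidence bounds, and "The estimates of the log(relative risk) and their standard errors for all the multiple imputation datasets will be input to PROC MIANALYZE". The p-value comes from that step.

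Neither document says what to do when a stratum or an arm has no responder. The one fallback, in SAP Section 9, covers convergence of the imputation model.

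**The concern.** The logit estimate is an inverse-variance average of stratum log relative risks. Each of these needs at least one responder in both arms. Early in treatment, vehicle responders may be few. Two of the three strata are capped at about 10% of subjects, and a baseline PGA 2 subject must reach PGA 0 to count as a PGA response.

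When a cell is empty, the estimate either does not exist or is set by whatever constant is added. The result given primary status could then miss a difference that the named CMH test would detect on the same data. These endpoints serve the secondary objective of describing efficacy over time. The dose rationale in Protocol 1.2 also remarks that "fast onset of action is an important consideration for topical medications".

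**Working it through.** **Inputs from the documents.** SAP Section 7 gives "approximately 333 subjects receiving tapinarof cream, 1% and approximately 167 subjects receiving vehicle cream". SAP Section 6 limits PGA 2 and PGA 4 to about 10% each, so the strata (tapinarof/vehicle) are about 33/17, 267/133 and 33/17. On alpha, SAP 11.1 says "All statistical tests will be performed at the 0.05 (two-sided) level of significance". There are 100 imputations (SAP Section 9).

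**Inputs assumed.** The early response rates, complete data, the same rate in every stratum, and the zero-cell constant (0.5 unless stated).

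**1. The plan's own power figures.** Two-sided Fisher exact power with 333 and 167 is above 99.9% at 40% vs 15% (stated: > 99%). At 35% vs 20% it is 93.8%, and 94.5% by a pooled z test (stated: > 94%). The figures are reproduced to within rounding and choice of method.

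**2. Chance of an empty vehicle arm, (1−p)^167.**
- 0.5%: 43%
- 1%: 19%
- 2%: 3.4%
- 3%: 0.6%

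This exceeds 5% only when p is below 1 − 0.05^(1/167) = 1.8%.

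**3. Chance of at least one empty vehicle stratum.** The formula is 1 − [1−(1−p)^17]² × [1−(1−p)^133].
- 1%: 1 − (1−0.843)² × (1−0.263) = 98%
- 2%: 1 − (1−0.709)² × (1−0.068) = 92%
- 3%: 84%
- 5%: 66%
- 15% (the Week 12 design rate): 12%

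**4. A worked table (assumed).** Tapinarof 17/333, as 1, 14 and 2 by stratum; vehicle 0/167.
- Without a constant, no common relative risk exists, logit or Mantel-Haenszel.
- With 0.5 added to each cell, the stratum RRs are (1.5/34)/(0.5/18) = 1.59, (14.5/268)/(0.5/134) = 14.5 and (2.5/34)/(0.5/18) = 2.65. The variances of the logs are 2.58, 2.06 and 2.32. The weighted mean log is 1.455 with SE 0.875, so RR = 4.3, z = 1.66 and p = 0.10.
- With constants 0.1 and 1, RR is 16.8 and 2.6, and p = 0.13 for both.
- CMH on the same table: expected 0.66 + 9.345 + 1.32 = 11.325; variance 0.224 + 3.006 + 0.440 = 3.670; z = (17 − 11.325)/√3.670 = 2.96; p = 0.003. The Mantel-Haenszel risk difference is 5.1 points (95% CI 2.7 to 7.5).
- A stratum with 0/33 and 0/17 would contribute RR (0.5/34)/(0.5/18) = 0.53, towards vehicle, from no events.

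**5. Simulated power** (200,000 trials per row; an undefined Mantel-Haenszel RR counts as not significant).

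| True rates | Logit RR, 0.5 fill | Mantel-Haenszel RR | CMH |
|---|---|---|---|
| 3% vs 1% | 0.4% | 3% | 25% |
| 5% vs 1% | 16% | 36% | 68% |
| 8% vs 2% | 59% | about 77% | 84% |
| 8% vs 3% | 40% | 56% | 62% |
| 12% vs 4% | 78% | 86% | 88% |
| 15% vs 5% | 90% | 94% | 95% |

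CMH rejects in 3.9% to 4.9% of null trials at rates of 1% to 3%, so its advantage is not bought with extra false positives.

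The loss does not depend on choosing 0.5. At 5% vs 1%, constants of 0.1 and 1 give 20% and 5%, and dropping zero-cell strata gives 10%. At 8% vs 2% the same three choices give 56%, 48% and 47%.

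**6. Where the loss comes from.** At 8% vs 2%, 18 of the 25 points (59 to 77, out of 59 to 84) disappear when the logit weighting is replaced by Mantel-Haenszel weighting. At 5% vs 1% only 20 of 52 points do; the rest is due to the relative-risk scale itself.

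**The case against.** - **The early rates are unknown.** No Week 2 or Week 4 rate is in the documents, and an empty vehicle arm is likely only below about 2%. It is least plausible for PASI-50, and for PGA 0 or 1, where a baseline PGA 2 subject needs one grade only. This stands, and a reader should not infer that the whole arm is expected to be empty. The commoner trigger is an empty small stratum.
- **The onset comparison survives.** A reader might infer that it is undefined. The documents do not support that. They also plan a log-rank test of time to PGA response, observed-case analysis of the same responder endpoints, ANCOVA of PASI and %BSA change at the same visits, and daily itch differences. None of these needs a log relative risk.
- **Little depends on it.** The endpoints are exploratory and outside the fixed sequence of SAP 11.6, and the remark on onset compares concentrations in a dose rationale. This stands and sets the severity.
- **The simulation is not the plan.** It uses complete data, equal rates and an assumed constant, and how the software treats zero cells is not stated. This is true. Other constants, or dropping strata, also lose heavily at these low rates.
- **The wording leaves room.** SAP Section 9 and Protocol 10.6 speak only of transforming results to a normal statistic, which would allow CMH pooling. That is so, but 12.8.1 is the only worked route and 12.8.2 points back to it.

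**Conclusion.** The point holds, as a minor one. Followed as written, the plan's primary MI analysis of the early responder endpoints can fail to produce an estimate, or can lose power against the test that 12.8.2 itself names. The loss is 52 points at 5% vs 1%, 25 at 8% vs 2% and 5 at 15% vs 5%. Above about a 2% vehicle rate most of it is due to the logit inverse-variance weighting; near 1% the relative-risk scale fails as well.

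These sizes rest on assumed rates equal across strata, complete data and a 0.5 fill.

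Two stronger inferences are not supported. A real early effect would not go unreported, since several unaffected analyses remain. Nor is the Week 12 conclusion threatened. A zero stratum can occur there too (12% at a uniform 15% vehicle rate; more often for PGA response if few vehicle subjects with baseline PGA 2 clear), but at 35% vs 20% the simulated power is 91.5% for the filled logit RR against 94.5% for CMH.

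**What to change.** In SAP 12.8.2, for the exploratory responder endpoints:

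1. Take the MI p-value from the signed square root of the PGA-stratified CMH statistic in each imputed dataset. Pool the 100 values, each with variance 1, by Rubin's rules. This fits the normal-statistic wording of SAP Section 9 and Protocol 10.6. State how an imputed dataset with no responder in either arm is handled.
2. Report MI-pooled response rates per arm, with the Mantel-Haenszel risk difference stratified by PGA and its 95% CI, also pooled by Rubin's rules.
3. Keep the relative risk as a descriptive measure where every imputed dataset has vehicle responders, for example at Week 8.

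The cost is a change of SAP wording and some programming, with no new data. The drawback is that the effect measure at sparse early visits differs from the relative risk at Week 12. Fixing this before unblinding also avoids choosing a zero-cell constant after seeing the results.
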